6.1.4 Adjustments for Covariates and Stratification

The randomization was stratified by disease subtype (MSA-P vs. MSA-C), diagnostic category (possible MSA vs. probable MSA), and country. Hence, treatment group comparisons of continuous efficacy endpoints will be adjusted by disease subtype, diagnostic category, and country. If there are sparse data within a stratum, then stratum may be combined.

The analysis of the primary endpoint and other continuous efficacy endpoints will also be adjusted by the baseline value of the endpoint as a covariate in statistical models.

6.2 Study Population

6.2.1 Analysis Sets

The number of subjects in each analysis set described in Section 4.1 is tabulated by asrandomized or as-treated treatment group (see Section 4.2), not randomized, and overall.

Inclusion and exclusion from the efficacy analysis set is tabulated by treatment group and overall, as the number and percentage of subjects in the randomized analysis set in both categories:

- Included in mITT population sample
- Excluded from mITT population sample (e.g., not treated, no baseline or no post-baseline efficacy data).

A by-subject listing of analysis sets is provided for the enrolled analysis set. The listing identifies subjects in analysis sets and includes as-treated treatment group.

A by-subject listing of subjects excluded from the efficacy analysis is provided for subjects in the mITT population who are not in the efficacy analysis set, including the reason for exclusion (i.e., not treated, no baseline or post-baseline efficacy data). Treated subjects may have > 1 exclusion reason.

A by-subject administrative listing of randomization scheme and codes is provided for all randomization numbers and block numbers, even those not assigned to a subject. This listing is sorted by randomization number and block number, and displays the randomization number, block number, site-subject ID, treatment group, randomization strata (i.e., disease subtype, diagnostic category, country), and randomization date.

6.2.2 Enrollment

Enrollment by (1) country and site and (2) age group are tabulated overall for the enrolled analysis set, where age group is based on age at informed consent.

A frequency table of accrual over time is also provided for the randomized analysis set. Time is randomization month and year based on the IWRS randomization date.

6.2.3 Subject Disposition

Subject disposition from enrollment to randomization is tabulated for the enrolled subjects as the number and percentage of subjects in the following categories:

- Number of screened subjects
- Number of subjects who failed screening and reasons for screen failure (e.g., withdrawal of
 consent, adverse event). For subjects whose reason for screen failure is due to
 inclusion/exclusion criteria not met, the inclusion/exclusion criteria will be included
- Number of rescreened subjects
- Number of subjects who failed rescreening and reasons for rescreen failures (e.g., withdrawal of consent, adverse event). For subjects whose reason for screen failure is due to inclusion/exclusion criteria not met, the inclusion/exclusion criteria will be included
- Number of randomized subjects.

Subject disposition for the double-blind phase is tabulated for the randomized subjects as the number and percentage of subjects in the following categories:

- Number of subjects who completed the double-blind phase
- Number of subjects who prematurely withdrew from the double-blind phase and reasons for withdrawal
- Number of subjects who continued into the OLE phase.

Subject disposition for the OLE phase is tabulated for the randomized subjects as the number and percentage of subjects in the following categories

- Number of subjects who continued into the OLE phase
- Number of subjects who completed the OLE phase
- Number of subjects who prematurely withdrew from the OLE phase and reasons for withdrawal.

A by-subject listing of study completion information for both the double-blind and OLE phase, including the reason for premature study withdrawal, if applicable, will be presented.

6.2.4 Protocol Deviations

Any event that does not comply with the inclusion/exclusion criteria, study conduct, or study procedures will be documented as a deviation.

The sponsor, or designee, will be responsible for producing the final protocol violation file (formatted as a Microsoft Excel file), which will be finalized prior to database lock. This file will include site, subject ID, deviation date, deviation type, a description of the protocol deviation, and its designation as a relevant protocol deviation or a significant protocol deviation.

Relevant protocol deviations are programmable deviations and include any event that does not comply with the inclusion/exclusion criteria, study conduct, or study procedures, and that significantly impacts the completeness, reliability, and interpretability of the study data. Relevant protocol deviations will be tabulated for the randomization and OLE phases, separately, and all relevant deviations will be presented in a by-subject listing.

A Microsoft Excel file of protocol deviations is extracted from the clinical trial management system (CTMS) by Biohaven Clinical Operations. This file serves as the raw data source of protocol deviations and classifies deviation severity as key and non-key. Significant protocol deviations are defined as those categorized as key deviations.

6.2.5 Baseline Characteristics

Baseline characteristics include (1) demographics and other relevant baseline characteristics, (2) medical and psychiatric history, (3) prior non-study medications, and (4) prior Parkinson's medications.

Baseline characteristics are tabulated for treated subjects, for subjects enrolled but not treated, and for Verdiperstat treated subjects.

Demographic and other baseline data will also be provided in by-subject listings.

Baseline is defined according to analysis set as follows:

- Enrolled but not treated: Last non-missing value
- Treated subjects: Last non-missing value at or before the study drug start date/time.

6.2.6 Extent of Exposure and Compliance to Study Treatment

Exposure and compliance are presented by as-treated treatment group and overall.

6.2.6.1 Study Therapy

Double-Blind Phase

For the double-blind phase, the extent of subject exposure (i.e., treatment duration) will be quantified as the number of days on study medication and measured from the time the subject received the first dose of study medication until the time the subject received the last dose of study medication. Treatment duration includes missed dose days; i.e., last dose date of double-blind randomized study medication – first dose date of double-blind randomized study medication + 1.

The extent of subject exposure (i.e., total days on study medication) will also be calculated for each subject by counting days where the number of tablets taken was > 0 (i.e., treatment duration – number of days a subject missed all doses of double-blind randomized study medication). If a subject took at least one dose of study medication on a study day, then the subject will be counted as having received study medication on that day.

Additionally, percent (%) compliance will be calculated as (total days on double-blind randomized study medication) / (treatment duration of double-blind randomized study medication) \times 100.

The number and percentage of subjects who had dose titrations during the double-blind phase will also be summarized by time point and dose.

Open-Label Extension Phase

For the OLE Phase, the extent of subject exposure (i.e., treatment duration) will be quantified as the number of days on study medication and measured from the time the subject received the first dose of study medication in the OLE Phase until the time the subject received the last dose, either at the end of the study or withdrawal from the OLE Phase. Treatment duration includes missed dose days, i.e., last dose date of OLE study medication – first dose date of OLE study medication + 1.

The extent of subject exposure (i.e., total days on study medication) during the OLE Phase will also be calculated for each subject by counting days where the number of tablets taken was > 0 (i.e., treatment duration – number of days a subject missed all doses of OLE study medication). If a subject took at least one dose of study medication on a study day, then the subject will be counted as having received study medication on that day.

Additionally, percent (%) compliance will be calculated as (total days on open-label Verdiperstat study medication) / (treatment duration of open-label Verdiperstat study medication) × 100.

The number and percentage of subjects who had dose titrations during the OLE phase will also be summarized by time point and dose.

Double-Blind and Open-Label Extension Phases Combined

For the combined phase data, the extent of subject exposure (i.e., treatment duration) to Verdiperstat during the entire study will be quantified as the number of days on study medication (Verdiperstat) and measured from the time the subject received the first dose of Verdiperstat until the time the subject received the last dose of Verdiperstat, either at the end of the study or withdrawal from the double-blind or OLE phases. Treatment Duration includes missed dose days within a study phase and excludes the dosing break between study phases (i.e., (last dose day of Verdiperstat study medication – first dose date of Verdiperstat study medication + 1) – (number of days with a dosing break between the double-blind and OLE phases)).

The extent of subject exposure (i.e., total days on Verdiperstat) during the entire study will also be calculated to exclude days when subjects missed a dose (i.e., Treatment Duration – number of days a subject missed all doses of study medication).

Additionally, percent (%) compliance will be calculated as (total days on Verdiperstat study medication) / (Treatment Duration of Verdiperstat study medication) × 100.

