² Subjects should be seated and resting for approximately 5 minutes prior to vital sign measurements - temperature, blood pressure, and heart rate. Tilt table may be used, if available.

³ Serum pregnancy test will be conducted in WOCBP (see section 5.5) at all scheduled visits. Urine pregnancy test will be performed on WOCBP (in addition to serum) at Baseline (within 24 hours prior to first dose).

CCI

CCI

⁶ One PK sample should be collected pre-dose and one PK sample should be collected post-dose. The time of the last BHV-3241/placebo dose prior to the sample collection and time of the PK sample collection and time of most recent meal should be reported on the CRF. At Weeks 4, 12, 24, 36 and 48, the morning dose of study drug should be held and administered in the clinic/office during the study visit, so that one pre-dose (trough) and one post-dose PK sample can be collected. The post-dose sample should be collected within a time window of approximately 2 to 4 hours. Collection of PK samples is not required at the Early Discontinuation visit.

CCI

⁸ Subjects should take the first dose of investigational product (IP) while in the office/clinic on the day of the Baseline visit and stay at the clinic for ~4 hours for observation. From start to end of Week 1, subjects will ingest either 300 mg QD of BHV-3241 or matching placebo QD. From start to end of Week 2, subjects will ingest either 300 mg BID of BHV-3241 or matching placebo BID. Starting with Week 3 and for the remainder of the double-blind portion of the study, subjects will ingest either 600 mg BID of BHV-3241 or matching placebo BID.

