7 STUDY DRUG MANAGEMENT

7.1 Description of Study Drug

7.1.1 *Investigational Product*

An Investigational Product (IP), also known as Investigational Medicinal Product in some regions, is defined as follows:

A pharmaceutical form of an active substance or placebo being tested or used as a reference in a clinical study, including products already with a marketing authorization but used or assembled (formulated or packaged) in a way different from the authorized form, or used for an unauthorized indication, or when used to gain further information about the authorized form.

The IP should be stored in a secure area according to local regulations. It is the responsibility of the Investigator to ensure that the IP is only dispensed to study patients. The IP must be dispensed only from official study sites by authorized personnel according to local regulations.

In this protocol, the IP is BHV-3241 300 mg tablets and matching placebo tablets.

The IP during the OLE phase of the study is BHV-3241 300 mg tablets.

7.1.2 *Packaging, Shipment and Storage*

The drug product is presented as BHV-3241 Extended Release (ER) Tablets that are reddish-beige, film coated and oval (300 mg strength). The tablets each consist of 300 mg of BHV-3241 drug substance as free base, and generally recognized as safe (GRAS) excipients for oral dosage forms including hydroxypropyl methyl cellulose, microcrystalline cellulose, hydroxypropyl cellulose, sodium stearyl fumarate and orange color. Matching placebo tablets contain microcrystalline cellulose and sodium stearyl fumarate and are film-coated with OPADRY® (mixture of hypromellose, polyethylene glycol and titanium dioxide) and iron oxide to give reddish-beige color. The tablets are packed in high-density polyethylene (HDPE) bottles. The bottles are induction sealed and closed with child resistant polypropylene (PP) screw caps.

All investigational products should be kept in a secure area with limited access under appropriate storage conditions. Container(s) of investigational product will bear a label containing (at a minimum) the name of the study drug, lot and/or batch number and appropriate storage conditions (15°-25°C [59°-77°F] in a tightly closed container, protected from light).

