7.4 Treatment Compliance

Responsible study personnel will dispense the study drug. Accountability and compliance verification should be documented in the subject's study records. Subjects will be counseled on the importance of taking the study drug as directed at all study visits.

Overnight shipment of study medication under ambient conditions (via certified and tracked courier and following Remote Visit Workaround Guidelines provided to sites), from the study site to study participants is permissible when an in-person study visit is not possible due to the COVID-19 public health emergency and if acceptable to the study site's institution. The sponsor should be consulted prior to shipping drug. Confirmation that the study drug shipment was received by the study participant should be retained as documentation, e.g., tracking confirmation printout from the courier, written documentation of contact with the subject (by phone, email, text), subject signature on packing list, etc.

If poor compliance continues, (i.e., taking study drug differently than per Investigator instructions, multiple missed doses resulting in less than 80% overall compliance), discontinuation of the subject from the trial should be considered and discussed with the Sponsor.

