3.2.1 Primary Objective Estimand

The estimands corresponding to the primary objectives for this study are shown in Table 1.

Table 1: Primary Objective Estimands

Objective	To evaluate the efficacy of Verdiperstat, compared to placebo, as measured by a change from baseline in a modified UMSARS score at Week 48
Efficacy Endpoint	Change from baseline in a modified UMSARS score at Week 48
Summary	Using the mITT population:
	 Descriptive statistics for modified UMSARS score and change from baseline as a continuous variable by treatment group at each visit
	 Difference in mean change from baseline in modified UMSARS scores between treatment groups at week 48 estimated and tested using a mixed-effect model for repeated measures (MMRM)
Intercurrent	1) Main Analysis - Observed data only
Events	2) Supplementary Analysis 1 – While on-treatment strategy
	3) Supplementary Analysis 2 – Compliant subjects hypothetical strategy
	4) Sensitivity Analysis – Multiple imputation jump to reference and copy increment from reference
	5) Sensitivity Analysis – Observed data only using narrower visit window for Week 48
Objective	To assess the safety and tolerability of Verdiperstat, relative to placebo, in subjects with MSA
Safety Endpoint	Frequency of unique subjects with serious adverse events (SAEs), AEs leading to study drug discontinuation, AEs related to study drug, clinically significant ECG abnormalities, and clinically significant laboratory test abnormalities
Summary	Number and percentage of subjects with safety events and findings for the safety population
Intercurrent Events	Treatment policy strategy, i.e., no accounting for intercurrent event

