6 STATISTICAL ANALYSES

6.1 General

6.1.1 Programmed Output

A separate document contains the list of all TLFs, along with corresponding templates, attributes, and programming notes.

All output will be sorted and labeled according to the International Conference on Harmonisation (ICH) recommendations and formatted to the appropriate page size(s).

Medical history and AEs are coded using Medical Dictionary for Regulatory Activities (MedDRA) Version 24.

Concomitant medications are coded using World Health Organization Drug Dictionary (WHO-DD), released March 2021.

All statistical analyses will be performed using SAS statistical software (Version 9.4 or higher), unless otherwise noted.

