6.3.2.2 Supplementary Analyses

The estimand for the first supplementary analysis will pursue a while on-treatment strategy. This will use the mITT population. The endpoint will be the change from baseline in the modified UMSARS score at the last measured time point. For subjects that stay on study, this will be the Week 48 visit. For subjects that discontinue early, the last on-treatment visit will be used as the endpoint. The population summary will be the difference between placebo and Verdiperstat treated subjects at their last visit. The summary will be computed using an Analysis of Covariance (ANCOVA), estimated by Restricted Maximum Likelihood (REML) that will include fixed effect factors for treatment group and randomization strata. Baseline modified UMSARS score will be used as a covariate.

The estimand for the second supplementary analysis will pursue a hypothetical strategy that estimates the effect of treatment in compliant subjects. The endpoint and population summary will be the same as used for the primary estimand. However, the population and handling of intercurrent events will be handled differently. The population will consist of subjects that are at least 80% compliant with the drug regimen and complete the Week 48 visit. In terms of intercurrent events, subjects that discontinue treatment, or are lost to follow-up, before Week 48 are not included in the analysis.

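### SAP percent compliance counts a day with any dose as fully compliant on a twice-daily regimen, and the 80% cut for the compliant-subject analysis has no definition of its own

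*SAP*

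**What the plan says.** SAP 6.2.6.1 obtains total days on study medication in the double-blind phase "by counting days where the number of tablets taken was > 0". It adds: "If a subject took at least one dose of study medication on a study day, then the subject will be counted" as on medication for that day. Only days on which every dose was missed are subtracted from treatment duration. Percent compliance is this day count over treatment duration, times 100. The open-label phase uses the same rule.

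The regimen is once daily in Week 1 only. Week 2 is 300 mg twice daily. From Week 3, footnote 8 of Protocol Table 1 has it that "subjects will ingest either 600 mg BID of BHV-3241 or matching placebo BID". Protocol 7.1.1 gives the tablet strength: "In this protocol, the IP is BHV-3241 300 mg tablets and matching placebo tablets". The full dose is therefore two tablets twice a day, which Protocol 7.2.2 states outright for the extension phase.

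SAP 3.2.1 (Table 1) lists supplementary analysis 2 of the primary endpoint as "Compliant subjects hypothetical strategy". SAP 6.3.2.2 defines its population: "The population will consist of subjects that are at least 80% compliant with the drug regimen and complete the Week 48 visit". It gives no formula and no reference to 6.2.6.1. Protocol 7.4 also uses 80%, as a trigger for considering discontinuation, and describes it as "multiple missed doses resulting in less than 80% overall compliance", again without a formula.

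**The concern.** On a twice-daily regimen, a compliance measure should fall when one of the day's two doses is missed. This one does not: any intake makes the day fully compliant. The score responds only to days with no intake at all.

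The consequence falls on supplementary analysis 2. Subjects who stop treatment or are lost before Week 48 are already excluded, so among completers the 80% cut is all that separates compliant from non-compliant. If the day ratio is used for the cut, the analysis can include subjects who took well under 80% of their assigned tablets, and its result would be reported as the effect in compliant subjects. The descriptive compliance summaries would overstate adherence in the same way.

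**Working it through.** The documents state no compliance result to reproduce, so the check applies the SAP formula and a tablet ratio to the same intake patterns.

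**Inputs**
- Duration: 48 weeks = 336 days, from the SAP and protocol design sections.
- Week 1: 7 days × 1 tablet = 7.
- Week 2: 7 days × 2 tablets = 14.
- Weeks 3–48: 322 days × 4 tablets = 1288.
- Planned tablets: 7 + 14 + 1288 = 1309.

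**Formulas**
- SAP compliance = days with at least one dose / 336.
- Tablet compliance = tablets taken / 1309.

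**Results.** The miss patterns are assumptions, and all misses fall on full-dose days unless stated.

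| Pattern | Tablets taken / planned | Tablet % | SAP days | SAP % |
|---|---|---|---|---|
| 67 whole days missed | (1309 − 268)/1309 = 1041/1309 | 79.5 | 269/336 | 80.1 |
| 34 whole days missed, plus one dose on 63 other days | (1309 − 136 − 126)/1309 = 1047/1309 | 79.98 | 302/336 | 89.9 |
| One dose missed on 130 days | (1309 − 260)/1309 = 1049/1309 | 80.14 | 336/336 | 100 |
| One dose missed on 131 days | (1309 − 262)/1309 = 1047/1309 | 79.98 | 336/336 | 100 |
| Evening dose missed every other day (161 days) | (1309 − 322)/1309 = 987/1309 | 75.4 | 336/336 | 100 |
| One full dose every day throughout | (7 + 7 + 644)/1309 = 658/1309 | 50.3 | 336/336 | 100 |

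The 131-day threshold is 131/322 = 40.7% of full-dose days, or 131/46 = 2.85 days a week. When only whole days are missed, the two measures agree closely. The gap comes entirely from within-day misses.

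**Sensitivity to duration.** At the 60-week maximum (420 days), planned tablets are 7 + 14 + 406 × 4 = 1645. One full dose a day then gives (7 + 7 + 812)/1645 = 826/1645 = 50.2%, still against 100% under the SAP.

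**Random misses.** Suppose each dose on a twice-daily schedule is missed independently with probability m (an assumption). The dose ratio is 1 − m and the day ratio is 1 − m². At m = 0.3 these are 70% and 91%. The day ratio falls below 80% only when m exceeds √0.2 = 0.447, where about 55% of doses are taken.

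**The case against.** The strongest point is that nothing in the SAP says the 6.2.6.1 ratio governs the 80% cut. Section 6.3.2.2 speaks of compliance with the regimen, which is twice daily, and the wording of Protocol 7.4 is in missed doses, so both lean towards a dose-based reading. A definition could also sit outside the two documents, since SAP 6.1.1 says: "A separate document contains the list of all TLFs, along with corresponding templates, attributes, and programming notes". This stands as a limit on certainty: the harm to supplementary analysis 2 is conditional on the day ratio being used. It does not rescue the text. If a dose-based measure was meant, the SAP has no formula for it, and its only compliance formula conflicts with the way the protocol describes the same threshold.

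Other points reduce the weight. The analysis is supplementary and outside the gatekeeping procedure. It is a completer subset selected after randomisation under any compliance measure. Sites assess compliance through the study and counsel subjects, and persistent compliance below 80% prompts consideration of discontinuation. That step is discretionary, so it lowers the chance of the extreme patterns without excluding them. All the patterns are hypothetical.

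The last objection concerns data. The SAP rule refers to tablets taken per day, but its equivalent form needs only the days with no intake. The documents describe no daily dosing diary and do not say that site accountability counts reach the analysis database. This stands, and the fix depends on confirming it.

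**Conclusion.** The concern holds. As written, percent compliance cannot fall because of within-day misses on a regimen that is twice daily for all but the first week, and the 80% cut in 6.3.2.2 is undefined. A subject taking about half the assigned tablets can score 100%. Mixed patterns give smaller gaps (79.98% of tablets against 89.9%), and whole-day misses give almost none.

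The defect in the formula and the absence of a definition for the cut are certain from the text. That the formula would be applied to the cut is an inference from its being the only one available. How many subjects would be misclassified is unknown, because the documents give no rate of partial-day dosing.

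The effect is confined to supplementary analysis 2 and the percent-compliance summaries. Treatment duration, day-count exposure, the primary MMRM, the key secondary tests, type I error and sample size do not depend on it. It should be corrected, but it does not threaten the trial's main conclusion.

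**What to change.** - In SAP 6.2.6.1, define percent compliance as tablets taken (recorded intake, or dispensed minus returned) divided by tablets prescribed over the treatment duration, times 100.
- Take the prescribed tablets from each subject's documented titration and approved dose modifications. State how the interruptions required by Protocol 4.3.1.1 and the dose holidays allowed by Protocol 8.1.8 enter the denominator.
- Cite this definition in SAP 6.3.2.2 for the 80% cut.
- Keep the day count, labelled as an exposure summary only.
- Editorially, in the combined-phase paragraph of 6.2.6.1, align the sentence about excluding days with a missed dose with its own formula, which removes only days with no dose at all. This has no bearing on supplementary analysis 2.

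The cost is SAP wording and a more involved derivation, because the denominator must follow extended titration, down-titration, re-challenge, holidays and interruptions. Protocol 7.2.3 and 8.1.8 require dose changes to be recorded, and Protocol 10.6 requires amounts dispensed and returned. The sponsor must confirm that these counts are available for analysis. If they are not, the minimum is to label the measure as day-based and say so in 6.3.2.2, so that the analysis does not claim more than the data support. Reported compliance and the compliant subset may be smaller after the change.
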